15.5 Secondary Objectives, Endpoints, Analysis Plans

The secondary objectives are to assess the effects of low dose apalutamide on 1) reversibility of testosterone levels 7-14 days post-intervention (post-operative), 2) post-intervention plasma trough apalutamide concentrations, and 3) health-related quality of life (HRQOL). The exploratory objectives are to determine the effects of apalutamide on intra-prostatic immune cell infiltration and Gleason score and the effects of tobacco/alcohol use on the study endpoints. The reversibility of testosterone levels will be measured by the change of testosterone levels from baseline to post operation. Paired t test will be performed on the changes in testosterone to evaluate the effects of low dose apalutamide for each dose group. Pearson correlation coefficient will be derived to evaluate the correlation between the plasma trough apalutamide levels and the change of PSA levels. HRQOL will be assessed by EPIC-CP. Changes in EPIC-CP (from baseline to end-of-intervention) in the overall score and sub-score for each measure will be derived and paired t test will be performed to evaluate the change for each dose group. Linear mixed effects model with a random intercept accounting within-subject dependence will be performed to compare the change in Gleason score of pre- and post-intervention tumor(s) since a participant can have more than one tumor. Changes in the Gleason score of pre- and post-intervention tumor(s) will also be assessed in a subgroup of participants where materials are available from pre- and post-intervention tumor(s) with matched location. The intra- prostatic immune cell infiltration will be measured by CD8⁺, CD4⁺, and CD56⁺ positive cells in the prostate tissues using immunohistochemistry. Changes (from most recent biopsy to prostatectomy) in these immune cells will be assessed for each dose group by paired t test. In addition, for changes in each of the secondary/exploratory endpoints a 95% CI will be reported for

each of the two dose groups. To explore the effects of tobacco/alcohol use on the endpoints, linear regression with tobacco/alcohol use and dose level indicators as the covariates will be performed for percent changes in PSA and change in EPIC-CP, CD8+, CD4+, and CD56+, respectively. Linear mixed effects model with tobacco/alcohol use and dose level indicators as the covariates will be fitted for the change in Gleason score. For each of the endpoints, the interaction effect between tobacco/alcohol use and dose level (i.e., effect modification or heterogeneity effect) will be tested, as well. If a significant interaction effect is detected, then subgroup analysis will be performed by dose level and reported accordingly.

Due to the exploratory nature of the secondary/exploratory endpoints, we are not planning to account for multiple comparisons but will interpret the findings carefully and report the total number of comparisons, which will then allow one to control for the false discovery rate (FDR) at a specific rate, say, $\leq 10\%$ via the adjusted p-value method. For both primary and secondary endpoints, data will be transformed before performing the test (paired t test or two-sample t test) if necessary. We do not anticipate observing any serious adverse events based on the dose levels considered for the study. At each study dose level, adverse events will be tabulated by the type of adverse events along with the associated 95% confidence intervals.

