4. PARTICIPANT SELECTION

4.1 Inclusion Criteria

4.1.1 Histologically confirmed organ-confined adenocarcinoma of the prostate (Pca) suitable for prostatectomy.

4.1.2 Gleason score \leq (4+4), however no Gleason pattern 5.

4.1.3 Current serum PSA \leq 20 ng/ml.

4.1.4 Age >18 years.

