9.2 Baseline Testing/Pre-Study Evaluation

At the screening/baseline visit, the informed consent form and medical records release form will be signed in order to obtain the biopsy/prostatectomy tissues, pathology reports and prior PSA test results. To minimize participant burden, remote consent may be implemented in compliance to the instructions in Appendix G. This visit will be scheduled between 7-10 AM, when feasible, for men $<$ 45 years of age and prior to 2 PM for men \geq 45 years of age because of circadian variation in testosterone levels. If the schedule is not feasible, the blood draw may be scheduled for another day. Participants will be evaluated for height, weight, and vital signs (temperature, pulse, and blood pressure), concomitant medications, medical history and baseline symptoms and signs. Baseline blood samples will be collected for CBC-diff, CMP, PSA, TSH, testosterone, and plasma apalutamide assay. Participants will also complete baseline tobacco/alcohol questionnaires and the Expanded Prostate Cancer Index Composite for Clinical Practice (EPIC-CP) questionnaire, and COVID-19 assessment. Subjects will be instructed on how to complete the Intake Calendar and Adverse Event Diary.

When eligibility is confirmed from lab results, participants will be provided with the study drug in amount sufficient for the entire study duration based on the surgery schedule and the assigned dosing regimen plus an extra week of agent supply. The study drug may be delivered to the subject by study staff or contracted courier. Participant may also pick up the study agent from the clinic.

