10. CRITERIA FOR EVALUATION AND ENDPOINT DEFINITION

10.1 Primary Endpoint

The primary endpoint is to determine the effects of low dose apalutamide on circulating levels of Prostate Specific Antigen (PSA). The percent change of PSA levels from baseline to end-of-intervention will be determined. If the prostate biopsy was performed within 6 weeks prior to the baseline visit, the most recent prior PSA instead of the PSA at the baseline visit will be used for the Baseline value. The proportion of participants with $\geq 25\%$ decline in PSA levels (from baseline to end-of-intervention) will be determined for each dose cohort.

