APPENDIX C
EXPANDED PROSTATE CANCER INDEX COMPOSITE FOR CLINICAL PRACTICE
(EPIC-CP)

- The EPIC-CP is a valid instrument that enables patient-reported health-related quality of life (HRQOL) to be measured efficiently and accurately in the routine clinical care of prostate cancer patients. The CRFs will be completed by the Site Staff or participant at the time of the designated visit.
- Data will be submitted as part of the final clinical data set.

EXPANDED PROSTATE CANCER INDEX COMPOSITE FOR CLINICAL PRACTICE (EPIC-CP)

REGISTERING INSTITUTION	PARTICIPANT ID	VISIT TYPE	VISIT DATE (MM/DD/YYYY)

Patients: Please answer the following questions by checking the appropriate checkbox. All questions are about your health and symptoms in the **LAST FOUR WEEKS**. Select one answer for each question.

1. Overall, how much of a problem has your urinary function been for you?
 No problem Very small problem Small problem Moderate problem Big problem

2. Which of the following best describes your urinary control?
0 Total control 1 Occasional dribbling 2 Frequent dribbling 4 No urinary control

3. How many pads or adult diapers per day have you been using for urinary leakage?
0 None 1 One pad per day 2 Two pads per day 4 Three or more pads per day

4. How big a problem, if any, has urinary dripping or leakage been for you?
0 No problem 1 Very small problem 2 Small problem 3 Moderate problem 4 Big problem

Clinicians: Add the answers from questions 2-4 to calculate the Urinary Incontinence Symptom Score (out of 12):

5. How big a problem, if any, has each of the following been for you?
a. Pain or burning with urination..... No problem Very small problem Small problem Moderate problem Big problem
b. Weak urine stream/incomplete bladder emptying... 0 1 2 3 4
c. Need to urinate frequently 0 1 2 3 4

Clinicians: Add the answers from questions 5a-5c to calculate the Urinary Irritation/Obstruction Symptom Score (out of 12):

6. How big a problem, if any, has each of the following been for you?
a. Rectal pain or urgency of bowel movements..... No problem Very small problem Small problem Moderate problem Big problem
b. Increased frequency of your bowel movements..... 0 1 2 3 4
c. Overall problems with your bowel habits..... 0 1 2 3 4

Clinicians: Add the answers from questions 6a-6c to calculate the Bowel Symptom Score (out of 12):

7. How would you rate your ability to reach orgasm (climax)?
0 Very good 1 Good 2 Fair 3 Poor 4 Very poor to none

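### Baseline EPIC-CP can carry symptoms of a recent biopsy, and the paired HRQOL analysis takes no account of biopsy timing

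*Combined protocol and SAP*

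**What the plan says.** - **Analysis (15.5).** "Changes in EPIC-CP (from baseline to end-of-intervention) in the overall score and sub-score for each measure will be derived and paired t test" is used to evaluate the change in each dose group. There is no control arm and no term for time since biopsy.
- **Recall period (Appendix C).** "All questions are about your health and symptoms in the" last four weeks, the form tells the patient. Items score 0 to 4 and higher is worse. Each of the five domains is out of 12, and the overall score is out of 60. Items include "Pain or burning with urination" and "Rectal pain or urgency of bowel movements", and the sexual domain asks about orgasm and erections.
- **Timing (9.1, 9.2, 9.4).** The form is completed at Visit 1 and Visit 2 only. Of Visit 1, section 9.2 says "Participants will also complete baseline tobacco/alcohol questionnaires and the Expanded Prostate Cancer Index Composite for Clinical Practice (EPIC-CP) questionnaire"; no condition on time since biopsy is attached.
- **Eligibility (4.1, 4.2).** Entry requires "Histologically confirmed organ-confined adenocarcinoma of the prostate (Pca) suitable for prostatectomy". Neither list sets a minimum interval from biopsy to enrolment.
- **PSA (10.1, repeated in 15.4).** "If the prostate biopsy was performed within 6 weeks prior to the baseline visit, the most recent prior PSA instead of the PSA" at that visit serves as baseline. No reason is given and no such rule exists for EPIC-CP.
- **Role of HRQOL (1.2, 2.3).** It is third in priority among the secondary objectives, and is meant to help inform whether low-dose apalutamide is feasible in active surveillance.

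**The concern.** Two Visit 1 measurements are used as baselines in the same men. For PSA, the plan sets the Visit 1 value aside after a recent biopsy. For EPIC-CP, it keeps the Visit 1 value even when the biopsy falls inside the questionnaire's recall period. If biopsy symptoms raise that baseline and have settled by Visit 2, their resolution is counted as change on apalutamide. Without a control arm, the two cannot be told apart.

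What is at stake is a conclusion that quality of life did not deteriorate when it did, or that it improved when it did not. For a drug being considered for men on active surveillance, missing a deterioration is the more costly error.

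**Working it through.** **No plan figure to reproduce.** The documents give no SD, meaningful change, power or sample size for EPIC-CP. The check therefore covers the timing, then the direction, then an illustration on stated assumptions.

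**1. Timing.** Study drug is supplied after Visit 1 laboratory results confirm eligibility (9.2), and planned intervention is at least 4 weeks (7.1). Visit 2 is within 3 days before surgery. In the shortest planned case, Visit 2 falls 28 − 3 = 25 days after the first dose, so its 28-day recall reaches back at most 3 days before that dose. The Visit 2 window therefore lies essentially after Visit 1 and does not cancel a raised baseline.

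**2. Domains exposed.** By item content these are urinary irritation (12 points), bowel (12) and sexual (12), which is 36 of the 60 points, and hence the overall score. The vitality/hormonal items (hot flashes or breast symptoms, depression, energy) have no evident link to biopsy.

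**3. Direction and size.** Let f be the share of men biopsied within four weeks before Visit 1, and d their excess baseline points beyond whatever persists at Visit 2. Then

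shift in mean (end − baseline) = −f × d.

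The shift is negative, toward improvement, and does not shrink with sample size. The documents give neither input. On assumed values:
- f = 0: 0
- f = 0.10, d = 1: −0.10 points
- f = 0.25, d = 3: −0.75 points
- f = 0.50, d = 6: −3.0 points

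**4. Effect on the test (illustration).** Express the excess as b, in SDs of the change score. Take n = 20 (the cohort maximum in 15.3), a two-sided 5% paired t test, and a true worsening of 0.660 SD, which gives 80% power when there is no bias. The mean shifts by −f×b and the SD becomes √(1 + f(1−f)b²).

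Worked case, f = 0.25 and b = 1.0: SD = √(1 + 0.25×0.75×1) = 1.090; standardised effect = (0.660 − 0.25)/1.090 = 0.377; noncentrality = 0.377×√20 = 1.68; power = 36%.

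| f | b (SD) | Shift (SD) | Power to detect the worsening | False significant improvement if no true effect (nominal 2.5%) |
|---|---|---|---|---|
| 0 | any | 0 | 80% | 2.5% |
| 0.10 | 0.5 | −0.05 | 73% | 4% |
| 0.25 | 0.5 | −0.125 | 60% | 7.5% |
| 0.25 | 1.0 | −0.25 | 36% | 16% |
| 0.50 | 1.0 | −0.50 | 9% | 48% |

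**5. Cost of excluding recent biopsies.** This removes the shift but reduces n. Power for the same 0.660 SD worsening falls from 80% (n = 20) to 75% (f = 0.10, n = 18), 66% (f = 0.25, n = 15) and 46% (f = 0.50, n = 10). A cohort that closes at 12 would keep 12 × 0.5 = 6 men at f = 0.50.

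**The case against.** The strongest reply is that the harm is not shown. Nothing in the documents says that biopsy raises EPIC-CP scores, how long symptoms last, or how many men enrol within four weeks. The PSA rule shows that biopsies within six weeks were foreseen, not how many fall within four; a man biopsied five weeks earlier triggers the PSA rule but lies outside the EPIC-CP recall. Section 15.5 already reports every sub-score, treats these endpoints as exploratory and promises careful interpretation. Escalation, de-escalation and cohort stopping use PSA response only (15.1). All of this stands, and it limits both the wording and the weight of the point.

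A reader might infer more than the documents support:
- *That the HRQOL test is biased.* That needs f and d above zero. Only that it can be biased follows.
- *That the PSA rule concedes the same problem for EPIC-CP.* The reason for the rule is not stated and the windows differ (6 weeks against 4).
- *That the whole HRQOL analysis is affected.* The vitality/hormonal domain has no evident exposure.
- *That the two cohorts will look different through their biopsy mix.* Section 15.5 plans no direct between-cohort HRQOL test; for EPIC-CP, dose level enters only the tobacco/alcohol regressions.
- *That the conclusion should rest on men without a recent biopsy.* That could leave very few men, and the lost power would itself make a deterioration easier to miss.

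What the reply does not remove is the gap. The analysis cannot show whether recent biopsy affected the result, although the date needed to find out must be collected for the PSA rule.

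**Conclusion.** The point holds as a possible bias of known direction and unknown size. It concerns the urinary-irritation, bowel, sexual and overall EPIC-CP changes in men biopsied within four weeks of Visit 1. The four-week recall, the Visit 1 timing, the absence of any biopsy interval or EPIC-CP adjustment, and the uncontrolled paired test are all in the documents. That biopsy symptoms raise these scores is an inference from item content.

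Under the assumed values above, the consequence runs from none (f = 0) through a modest loss of power (80% to 73%) to a test that mostly misses a real worsening (9%). The documents do not allow a choice within that range. This is a minor point: it touches a third-priority secondary endpoint and no dose decision. It merits action because the safeguard costs almost nothing.

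**What to change.** In 15.5, keep the paired analysis in all men as the main HRQOL analysis and add:

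1. The overall and domain EPIC-CP changes, with 95% intervals, reported separately for men biopsied within 4 weeks before Visit 1 and for the others.
2. A pre-specified sensitivity analysis for the urinary-irritation, bowel, sexual and overall scores that adjusts for recent biopsy (yes/no) or excludes those men. The adjusted estimate to report is the mean change in men without a recent biopsy.
3. A sentence stating that a conclusion of no deterioration in those scores must be consistent with the sensitivity analysis. The vitality/hormonal domain is read from all men.

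The cost is a few lines of text. The PSA rule already requires the biopsy date, so no new data or visits are needed. The downside is small subgroups and wide intervals, so the sensitivity analysis will often be imprecise and should be read by estimate and interval, not by its p-value.

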National Cancer Institute, Division of Cancer Prevention
[name]
[name]
[contact]
[contact]
[contact]

Scientific Lead: [name]
National Cancer Institute, Division of Cancer Prevention
[name]
[name]
[contact]
[contact]

Nurse Consultant: [name], BSN
National Cancer Institute, Division of Cancer Prevention
[name]
[name]
[contact]
[contact] (fax)
[contact]

IND Sponsor: NCI/Division of Cancer Prevention

IND# [REDACTED]

Agent(s)/Supplier: Apalutamide/commercial sources

Protocol Version Date: 04/04/2023

**Protocol Revision or
Amendment #** Version 6.8

SCHEMA

Clinical Study of Bioactivity of Low Dose Apalutamide in Prostate Cancer Patients Scheduled for Prostatectomy

Men with histologically confirmed organ-confined adenocarcinoma of the prostate scheduled for prostatectomy;
Gleason score \leq (4+4=8) and current serum PSA \leq 20 ng/ml.

Visit 1 - Screening/Baseline Visit

Informed consent; medical records release form to obtain the biopsy/prostatectomy tissues, pathology reports and prior PSA test results; medical history; concomitant medications; baseline signs and symptoms; Karnofsky performance status; height; weight; vital signs; blood for clinical labs, PSA, TSH, testosterone, and plasma apalutamide assay (the blood draw for testosterone should occur between 7-10 AM for men $<$ 45 years of age and prior to 2 PM for men \geq 45 years of age. If the schedule is not feasible, the blood draw may be scheduled for another day); baseline tobacco/alcohol questionnaires, the Expanded Prostate Cancer Index Composite for Clinical Practice (EPIC-CP) questionnaire, and COVID-19 assessment.

Agent Initiation

The study is expected to have 2 dose groups. Participants in the first dose group will receive apalutamide 60 mg MWF for 4-8 weeks prior to prostatectomy. Based on the PSA response, an additional group of participants will receive de-escalated dose at 60 mg once per week, or escalated dose at 60 mg daily for 4-8 weeks prior to prostatectomy. **For each dosing regimen, the participant will take a loading dose (3 x 60 mg) the first day of agent intervention to reach the steady-state drug levels sooner.** Participants may receive the agent intervention up to 12 weeks if the surgery is delayed.

Participant Contact

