Patients with Gleason score 8 are included because we expect the PSA response (and the response of other study endpoints) to low dose apalutamide to be similar to patients with Gleason score 6 and 7. However, any Gleason pattern 5 is an exclusion. The prior Phase I study in patients with castration-resistant prostate cancer showed that apalutamide taken at 60 mg per day resulted in steady-state plasma trough apalutamide concentrations similar to plasma concentrations observed at a dose level that led to tumor growth inhibition in the murine model of castration-resistant prostate cancer [8]. We have, therefore, selected to study the 60 mg dose at different dosing schedules up to 60 mg per day. Due to the anticipated short intervention period (4-8 weeks, depending on the surgery schedule), pharmacokinetic simulations were performed to select optimal loading dose to reach steady-state drug levels sooner to increase the likelihood of observing the drug effects. Figure 1 illustrates the plasma trough levels over time with a loading dose of 180 mg for three maintenance dosing schedules (data generated by [name], NCI Clinical Pharmacology Program). A loading dose of 180 mg for the 60 mg once a day dosing schedule will reach steady-state levels at the end of 2 weeks. Similar time to steady-state is achieved with a loading dose of 180 mg for the 60 mg q M-W-F dosing schedule. A loading dose of 180 mg for the 60 mg once a week dosing schedule will allow the target level to be achieved and maintained after the first dose.

A recently completed trial of enzalutamide in prostate cancer patients with biochemical recurrence showed that elevated testosterone levels with enzalutamide treatment decline rapidly following discontinuation of enzalutamide (personal communication provided by NCI, DCP). This study will assess the reversibility of circulating testosterone levels after low dose apalutamide. We also plan to assess the plasma trough apalutamide levels and to determine whether the systemic drug levels correlate with the PSA response.

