10.3 Exploratory Endpoints

- Gleason score of pre- and post-intervention tumor(s). Changes (from most recent biopsy to prostatectomy) in the Gleason score of pre- and post-intervention tumor(s) will be assessed for each dose group. Changes in the Gleason score of pre- and post-intervention tumor(s) will also be assessed in a subgroup of participants where materials are available from pre- and post-intervention tumor(s) with matched location. It is expected that such matched materials will only be available in a subgroup of participants where pathology review can be performed on *ex vivo* prostate tissue sample collected at prostatectomy from the tumor(s) that MRI directed biopsies were collected prior to enrollment.
- Intra-prostatic immune cell infiltration. CD8 $^{+}$, CD4 $^{+}$, and CD56 $^{+}$ positive cells in the prostate tissues will be assessed by immunohistochemistry. Changes (from most recent biopsy to prostatectomy) in these immune cells will be assessed for each dose group. Changes in immune cell infiltration will also be assessed in a subgroup of participants where materials are available from pre- and post-intervention tumor(s) with matched location.

The effects of tobacco/alcohol use on the study endpoints will be assessed by examining the associations between tobacco and alcohol consumption and the effects of apalutamide on the study endpoints.

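### Gleason change is analysed on what reads as a total score, and the unmatched biopsy-to-prostatectomy comparison can show sampling differences as drug effect

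*Combined protocol and SAP*

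**What the plan says.** Section 1.3 makes it an exploratory objective to determine the effect of apalutamide on Gleason score.

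- **Comparison.** Section 10.3: "Changes (from most recent biopsy to prostatectomy) in the Gleason score of pre- and post-intervention tumor(s) will be assessed for each dose group". It adds a second assessment in tumours matched for location, and warns: "It is expected that such matched materials will only be available in a subgroup of participants". Section 15.5 keeps the same order, with the matched analysis as an addition.
- **Rationale.** Section 2.3 describes the Gleason question only in terms of tumours with matched location. Section 12.2 asks for matched slides or blocks when available.
- **Model.** Section 15.5: "Linear mixed effects model with a random intercept accounting within-subject dependence will be performed to compare the change in Gleason score", with the random intercept justified "since a participant can have more than one tumor". A second model uses the same outcome: "Linear mixed effects model with tobacco/alcohol use and dose level indicators as the covariates will be fitted for the change in Gleason score". Section 15.5 also promises a 95% CI per dose group for changes in each exploratory endpoint.
- **Scale.** The coding of the score is not stated. The Schema writes the entry limit as 4+4=8. Section 2.3 expects the PSA response of men with score 8 "to low dose apalutamide to be similar to patients with Gleason score 6 and 7". Grade group, coding by primary and secondary pattern, and an ordinal model are not mentioned.
- **Entry.** Section 4.1 limits the score to 4+4, "however no Gleason pattern 5".
- **Control.** Sections 7.1 and 8.8: every cohort receives apalutamide, and there is no randomisation.

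**The concern.** A linear model needs a numeric outcome, and the number the documents attach to Gleason score is the total. That total does not distinguish 3+4 from 4+3, in a trial that section 2.3 describes as being in low- and intermediate-risk disease. A change in the predominant pattern, in either direction, would be recorded as no change.

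The second issue is what the change measures. Needle cores sample part of the gland and the prostatectomy specimen is all of it, so the two grades can differ without any treatment. Without location matching, the tumours compared need not be the same ones. The random intercept allows for correlation among tumours within a man; it neither pairs tumours nor removes a sampling difference. With no untreated group and no reference upgrade rate, the estimate cannot separate sampling from drug.

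At stake is the reading of one exploratory endpoint. A sampling shift could be reported, with a confidence interval, under an objective worded as the effect of apalutamide, while a real improvement from 4+3 to 3+4 would go unseen.

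**Working it through.** The documents give no sample size, SD, effect size or upgrade rate for this endpoint, so there is no stated figure to reproduce. From the documents: up to 20 men per dose group (15.3), the linear model (15.5), the entry limit (4.1). Every rate below is an assumption.

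**1. Scale.** This step needs only the score definitions.

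| Biopsy to prostatectomy | Change in total | Change in grade group |
|---|---|---|
| 3+3 to 3+4 | 7 − 6 = +1 | 2 − 1 = +1 |
| 3+4 to 4+3 | 7 − 7 = 0 | 3 − 2 = +1 |
| 4+3 to 3+4 | 7 − 7 = 0 | 2 − 3 = −1 |
| 4+3 to 4+4 | 8 − 7 = +1 | 4 − 3 = +1 |

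The data transformation that 15.5 allows cannot help, because no transformation of 7 separates 3+4 from 4+3.

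**2. Men affected by the scale.** Formula: 20 × share with Gleason 7 × share of those who move between 3+4 and 4+3.
- Share 60%, movement 15–25%: 12 × 0.15 = 1.8 to 12 × 0.25 = 3.0 men per cohort scored zero.
- Share 40–80%, same movement: 8 × 0.15 = 1.2 to 16 × 0.25 = 4.0 men.

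**3. Sampling.** Mean change = (one-point upgrades − one-point downgrades) / 20.
- 4 up, 0 down: +0.2.
- 4 up, 2 down: +0.1.
- 4 up, 4 down: 0.

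The shift depends on net under-grading at biopsy.

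**4. Null simulation.** 20 men, no drug effect, one tumour each. A two-sided 5% one-sample t test on the change in total stands in for the mixed model. Biopsy grade is wrong by one category at the stated rates. Two true-grade mixes were used for 3+3, 3+4, 4+3, 4+4 and any pattern 5 (scored 9): 25/40/20/12/3% and 10/35/30/17/8%. Ranges cover both mixes; the nominal upper-tail rate is 2.5%.

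| Biopsy error | Entry cap | Mean change in total | Runs with a significant rise |
|---|---|---|---|
| Symmetric, 10% or 20% each way | no | −0.005 to +0.006 | 0.9–2.8% |
| Symmetric, same | yes | +0.010 to +0.044 | 1.1–6.0% |
| Under-graded 20–40%, over-graded 10–15% | no | +0.053 to +0.183 | 6.3–32.1% |
| Under-graded, same | yes | +0.068 to +0.214 | 8.4–43.8% |

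- Cap versus no cap, scenario by scenario: the difference runs from 0.010 − (−0.002) = 0.012 to 0.044 − 0.006 = 0.038 points. The cap is a minor contributor; net under-grading drives the shift.
- With the cap, 31–39% of category differences lay between 3+4 and 4+3 and scored zero, so 61–69% did register on the total.
- In the under-graded scenarios with the cap, mean change in grade group was +0.068 to +0.305. A better scale does not remove the sampling shift; that needs the matched set and the right label.

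**The case against.** **The scale is inferred.** Section 15.5 never writes that the sum is used, and 4.1 shows that component patterns are known at entry. A reader might infer that the plan specifies the sum. It does not: the total is the natural reading of a linear model plus the Schema and section 2.3. If grade group is intended, the 3+4 versus 4+3 point falls, but the text should say so; the sampling point stays.

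**Matching is already planned.** This largely stands. Sections 2.3, 10.3, 12.2 and 15.5 all provide for it, so it would be wrong to say the plan overlooks it. What remains is that 10.3 and 15.5 do not say which comparison carries the interpretation.

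**The entry cap.** One might infer that capping the biopsy but not the surgical grade produces a material false rise. The cap does act upward, but by about 0.01 to 0.04 points under the assumptions above. A note is enough.

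**The tobacco/alcohol model.** One might infer that its coefficients are biased as well. A sampling shift common to all men goes into the intercept; it biases those coefficients only if sampling error differs by tobacco or alcohol use, and nothing in the documents suggests that. That model does share the scale problem.

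**Direction.** Net under-grading pushes the change upward, so it would look like harm or hide a benefit rather than create one. If every surgical focus were counted, small low-grade foci missed at biopsy could pull the other way. The direction is therefore not certain.

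**Low stakes.** The endpoint is exploratory and 15.5 promises careful interpretation. That stands, although the promise is made about multiple comparisons, not measurement.

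**Conclusion.** The point holds as a low-cost improvement to an exploratory endpoint: nice to have, not a required correction. On the total scale, shifts between 3+4 and 4+3 are invisible, which under the assumed rates means roughly 1 to 4 men per cohort of 20. The unmatched, uncontrolled comparison can show a rise without any drug effect: +0.05 to +0.18 points from net under-grading alone, and +0.07 to +0.21 with the entry cap. These sizes rest on assumed grade mixes and error rates, one tumour per man, and a t test in place of the mixed model. The scale and comparison points follow from the documents' text; the scale point is conditional on the total being what is meant.

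Two stronger conclusions are not supported. The matched-location set would not isolate a drug effect, because it still has no control arm and its size is not stated. Nor does this reach the primary PSA result or the dose decision, which section 15.1 bases on PSA response alone.

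**What to change.** In sections 10.3 and 15.5:

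1. Derive the five-level grade group from the primary and secondary patterns in the biopsy and surgical pathology reports that section 9.5 already collects.
2. Report the numbers upgraded, unchanged and downgraded per cohort, stating whether men or tumours are counted.
3. Treat grade group as ordinal in any model, including the tobacco/alcohol model. Putting the five levels into the same linear model would still assume equal intervals.
4. Align both sections with 2.3 by basing interpretation on the matched-location set, described as uncontrolled and exploratory.
5. Label the unmatched biopsy-to-prostatectomy change descriptive, not an effect of apalutamide, with one sentence noting the entry cap.

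The cost is wording and one derived variable, provided the reports and the matched pathology review record both patterns; no slides need re-reading for this. The downside is that the interpreted set has fewer participants, so its results will be less precise.
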